## Objectives

This prospective randomised trial aims to test if Virtual Reality (VR) simulation helps medical students who have no surgical experience acquire basic surgical skills in total hip arthroplasty (THA) by performing two difficult THA steps: the acetabular cup and femoral stem implantation in a specific position. This study hypothesised that VR training could help young doctors orient themselves in space and perform more accurate cup implantation in 60° inclination and femoral stem in 20° anteversion than a control group that had only video teaching from an expert. The primary outcome will be the a. the difference in the mean implanted cup inclination and femoral stem anteversion between the VR and control group b. the mean difference between the asked predefined and the actual implanted cup inclination or cup version between the VR and control groups. Secondary outcomes will be other differences in completing the task between groups a. the time needed to complete the task and b. the times asking for assistance c. the number of mistakes.

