#### Video teaching

All medical students were then asked to watch a detailed video explaining the basic anatomy of the hip joint, the fundamental pathophysiology of hip arthritis, and the THA steps. The video explained in detail the necessary steps and basic rules that the surgeon must understand to implant the acetabular cup and femoral stem in a proper position. The video was focused on practices and methods to understand the intraoperative landmarks to achieve a cup inclination of 30-60° and stem anteversion of 20° during implantation. All participants were free to watch the video two to three times to thoroughly understand the principles of the cup and femoral stem implantation.

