#### Randomisation

All participants were then randomised in the VR or control group for cup and stem training and implantation by a computerised random number generator. In detail, each participant was randomised in the VR group for the cup or the stem implantation but in the control group for the other part of the THA. So, participants enrolled on the VR group for cup training were the control group for the femoral stem training and vice versa. In this way, each participant was asked to do one implantation following VR training and the other without VR training. Participants were privately notified of their randomisation assignment and asked not to disclose their designated cohort with any other study participant or research personnel. Only a research team member

knew of the cohort assignments during this study. This study personnel did not participate in the evaluation and analysis of data.

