#### VR training

As mentioned, each participant was randomised and did one implantation, either the acetabular cup or the femoral stem, following VR training and the other (stem or cup) without VR training, respectively. This method allowed us to evaluate and compare the performance of participants who received VR training versus those who did not within the same implantation. It also enables us to assess individual participants' performance in both scenarios (stem or cup), with and without VR training.

Before the VR-THA training, participants were asked to complete a survey evaluating their previous VR technology experience. All VR group participants were then asked to complete three consecutive VR sessions using the VR system (ORama VR, Geneva, Switzerland), performing cup or stem implantation based on their group.

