#### Saw bone simulation

After completing VR training, all participants were asked to implant the cup at a 60° inclination in sawbones and the femoral stem at 20° of anteversion. As mentioned, they performed one implantation following VR training and the other without VR training.

[figure not shown]
The sawbones had been reamed and prepared appropriately to accommodate the metal prostheses from the students steadily. The students did not perform any reaming to the sawbones. The same saw bone was used for several implantations but was replaced with a new one when it could no longer handle the implant properly. The cup inclination and stem version were evaluated using specific goniometers and assessment of photographs taken during implantation. During implantation in sawbones, a study assistant was present and was instructed to intervene only if the study participants requested assistance or could not progress through the task.

Upon completion of the VR-THAs, participants completed a survey focused on their interest in using VR simulations for surgical skills training and assessing potential negative consequences.

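### The hypothesis names a video-only control group, but on the stated order every control had already had VR training on the other component

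*Combined protocol and SAP*

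**What the plan says.** The hypothesis in the Objectives is that VR-trained students will place the cup and stem more accurately "than a control group that had only video teaching from an expert". The mechanism it offers is that "VR training could help young doctors orient themselves in space".

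The Methods describe the following procedure.

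- **Video teaching:** "All medical students were then asked to watch a detailed video". Everyone receives the video, before randomisation.
- **Randomisation:** "participants enrolled on the VR group for cup training were the control group for the femoral stem training and vice versa".
- **VR training:** the VR group for each component completes three consecutive sessions on that component. The design is said to allow the trial to "compare the performance of participants who received VR training versus those who did not within the same implantation", and also to assess each student's "performance in both scenarios (stem or cup), with and without VR training".
- **Saw bone simulation:** "After completing VR training, all participants were asked to implant the cup at a 60° inclination in sawbones and the femoral stem". The same section adds that "they performed one implantation following VR training and the other without VR training".

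The SAP compares the groups with an independent-samples t-test (Mann-Whitney U if the data are not normal). It also compares each student's outcomes with and without VR by a paired t-test. Neither the Methods nor the SAP mentions carry-over from one component to the other.

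**The concern.** The comparator in the hypothesis is not the one the Methods describe. A cup control has watched the video and, on the stated order, has also completed VR training on the stem before placing the cup. The reverse holds for stem controls. These students had video only for the component being tested, but they were not untouched by VR.

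This affects what a result would mean. If VR gives a general gain, which is how the plan's own mechanism reads, part of that gain reaches the controls, and the observed difference understates VR versus video only. If training on one component interferes with the other, the difference overstates it. A null result is the most exposed: it could mean that VR adds nothing, or that both groups gained from it.

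The paired test has a related labelling problem. For each student it compares the VR-trained component with that student's other component, so the label of with and without VR does not fully describe it.

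**Working it through.** **1. What each group had received before the sawbone test, on the written order**

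| Component tested | Group | Video | VR on tested component | VR on other component |
|---|---|---|---|---|
| Cup | VR | yes | yes | no |
| Cup | Control | yes | no | yes (stem) |
| Stem | VR | yes | yes | no |
| Stem | Control | yes | no | yes (cup) |

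No row has the video and no VR at all, so the group named in the hypothesis does not occur.

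**2. What the between-group difference estimates**

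Let μ be the mean after video only, τ the effect of VR on the tested component relative to video only, and c the share of τ that VR on the other component carries over.

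- VR group mean = μ + τ
- Control group mean = μ + cτ
- Difference = τ(1 − c)

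This equals τ only if c = 0. The trial has two group means per component and three unknowns (μ, τ, c), and no VR-free group from which to estimate μ. The value of c therefore cannot be estimated or tested from its data.

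**3. Illustration of size, mean cup angle only**

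Inputs from the documents: difference 20°, SD 18° and two-sided alpha 0.05 (Power Analysis); 101 enrolled (Recruitment).

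Assumptions, not in the documents: a 50/51 split; c from −0.25 to 0.5; and that the planned 20° means VR versus video only.

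The plan's own sample size plays no part here. For the record, its inputs give 2 × (1.960 + 0.842)² × (18/20)² = 12.7, or 13 per group and 26 in total, whereas the plan states 26 per group. The illustration uses the number enrolled instead.

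- Standard error = 18 × √(1/50 + 1/51) = 3.58°
- Shift for each 0.1 of c = 0.1 × 20° = 2°, and 2/3.58 = 0.56 standard errors
- Power is from the noncentral t distribution with 99 degrees of freedom and noncentrality 20(1 − c)/3.58

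| c | Expected difference | Power |
|---|---|---|
| −0.25 | 25° | >99.9% |
| 0 | 20° | >99.9% |
| 0.1 | 18° | 99.9% |
| 0.25 | 15° | 98.6% |
| 0.5 | 10° | 78.9% |

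Power falls to 80% at a difference of 10.13°, that is at c = 1 − 10.13/20 = 0.49.

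The documents give no SD for the stem or for deviation from the requested angle, so no such table can be made for those outcomes.

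**The case against.** The strongest reply is that the crossed allocation is fully disclosed. Randomisation, VR training and Saw bone simulation each repeat that a student did one implantation after VR training and one without it. A reader can work out the control condition, and the phrase in the Objectives may be only a compressed summary. For the tested component, controls did have video only. This stands as far as disclosure goes. It does not supply the missing assumption, and the hypothesis still names a different comparator.

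Second, the order rests on one sentence. The same section says the other implantation was done without VR training, and the design figure was not available for this review. This also stands, and it limits confidence. The remark about no VR training fits the reading of no VR on that component, but testing controls before any VR session is not excluded. In that case the order sentence is what needs correcting.

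Third, no consequence is demonstrated. The existence, sign and size of carry-over are all assumed, the VR sessions were component-specific, and the two target angles differ. Power stays high except at large carry-over, and positive carry-over only makes the test conservative. The illustration concerns a difference in mean angle, whereas the hypothesis is about accuracy, and a gain in accuracy need not shift the mean in proportion. All of this is fair, and the figures should be read as illustration, not evidence. The main point is not loss of power, however, but which comparison the result describes.

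The paired-test label is a smaller matter, because the VR training section already says that the two scenarios are stem and cup. It does not add to the weight of the point.

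**Conclusion.** The concern holds. As written, the plan attributes to its control group a property, video teaching only, that the described procedure does not deliver. The randomised contrast within each component remains valid and supports a conclusion about component-specific VR training. Reading it as VR versus video only, including reading a null result that way, requires no carry-over between components. The plan does not state that assumption and the design cannot test it.

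The size is unknown. On the cup-angle illustration the effect ranges from nothing (c = 0, or if 20° was already meant as this design's contrast) to a halving of the expected difference at c = 0.5.

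The point should be addressed, with medium confidence. It depends on the written order of VR training before both implantations, which one sentence establishes.

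**What to change.** 1. In the Objectives, the hypothesis and the SAP, define the control for the between-group tests as: video teaching, no VR training on the tested component, VR training on the other component.
2. Limit the conclusion to component-specific VR training. Add a limitation stating that reading it as VR versus video only, including for a null result, assumes no carry-over between components, which the design cannot test.
3. Describe the paired t-test separately, as a comparison of a student's VR-trained component with the same student's other component.
4. State explicitly the order of the VR sessions and both sawbone implantations.
5. If control implantations were in fact done before any VR session, correct the opening sentence of the Saw bone simulation section instead. The comparator wording in the Objectives would then stand.

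This changes wording only: no new data, test or sample size is needed. The cost is a narrower claim.

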## Background

All residents traditionally acquire new surgical skills by carefully studying technique guides, diligently watching procedure videos and working closely with a mentor. However, according to a study, 96% of residents independently learned how to prepare for surgical procedures. A recent study revealed that less than 80% of general surgery residents who have completed their training were competent in performing complex yet standard medical procedures on patients. This emphasizes the importance of looking into additional training methods to fill the gap in surgical education.

There are currently a few surgical training methods, including reading surgical technique guides, using sawbones simulations, and performing cadaveric dissection. However, each of these methods has its limitations. Sawbones simulation is limited and not reusable, while cadaveric dissections are expensive, time-consuming and only provide little practice. Basic equipment knowledge is necessary to use technique guides, but practical exercises may not be possible.

Hence, it's crucial to integrate simulation into medicine, specifically in orthopaedics. VR technology has been evaluated as a training method for medical doctors or junior surgeons with promising results in their respective fields of expertise. Although VR technology is advancing rapidly, there is still a limited number of high-level studies on how it can be used to train surgeons. It is still being determined whether surgeons using VR gain advantages in identifying anatomical structures, understanding the steps involved in a procedure, improving their skills during difficult stages of a task, or more efficiently navigating themselves during surgery.

## Methods

This study is a prospective randomised controlled trial with a specific design (*figure 1*) which is detailed below.

#### Recruitment

This prospective randomised trial was approved by our Institutional Review Board (70/2023-15/02/2023). Eligible study participants included undergraduate medical students at our university with no previous surgical experience willing to participate. Exclusion criteria included a. postgraduate medical students b. prior experience in THA or general surgery, c. undergraduate students unwilling to participate.

One month before the planned VR-THA surgery session, all eligible medical students were invited to an information session regarding the study through the university's social media. The 101 medical students who fulfilled the inclusion criteria were voluntarily enrolled, providing informed consent.

#### Pretest

Immediately after enrollment, medical students were asked to complete a multiple-choice pretest to quantify their baseline medical and procedural knowledge of hip arthritis and THA. All participants were unaware and unable to prepare for the pretest assessment, which allows the test scores to be considered an accurate measure of baseline knowledge.

#### Video teaching

All medical students were then asked to watch a detailed video explaining the basic anatomy of the hip joint, the fundamental pathophysiology of hip arthritis, and the THA steps. The video explained in detail the necessary steps and basic rules that the surgeon must understand to implant the acetabular cup and femoral stem in a proper position. The video was focused on practices and methods to understand the intraoperative landmarks to achieve a cup inclination of 30-60° and stem anteversion of 20° during implantation. All participants were free to watch the video two to three times to thoroughly understand the principles of the cup and femoral stem implantation.

#### Randomisation

All participants were then randomised in the VR or control group for cup and stem training and implantation by a computerised random number generator. In detail, each participant was randomised in the VR group for the cup or the stem implantation but in the control group for the other part of the THA. So, participants enrolled on the VR group for cup training were the control group for the femoral stem training and vice versa. In this way, each participant was asked to do one implantation following VR training and the other without VR training. Participants were privately notified of their randomisation assignment and asked not to disclose their designated cohort with any other study participant or research personnel. Only a research team member

knew of the cohort assignments during this study. This study personnel did not participate in the evaluation and analysis of data.

#### VR training

As mentioned, each participant was randomised and did one implantation, either the acetabular cup or the femoral stem, following VR training and the other (stem or cup) without VR training, respectively. This method allowed us to evaluate and compare the performance of participants who received VR training versus those who did not within the same implantation. It also enables us to assess individual participants' performance in both scenarios (stem or cup), with and without VR training.

Before the VR-THA training, participants were asked to complete a survey evaluating their previous VR technology experience. All VR group participants were then asked to complete three consecutive VR sessions using the VR system (ORama VR, Geneva, Switzerland), performing cup or stem implantation based on their group.

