#### Power Analysis

After reviewing eight recent RCT studies on virtual reality simulation training, it was found that each study had an average of 14 to 28 participants and an effect size of 0.80 to 0.90. Previous studies have utilised specific scores to evaluate the impact of trauma or arthroplasty simulator training on actual performance in real-world scenarios. These evaluations were different from our measurements. To assess the necessary sample size for our study, we based on the first ten measurements of cup angle implantation from our medical students; the mean cup angle was 50.40 with a standard deviation of 18°. To detect a difference of 20 degrees of implantation

between two groups with a standard deviation of 18 degrees and with a two-sided alpha of 0.05 and power of 80%, at least 26 students were required in its group.

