**Figure 1, Study Design**

### **Statistical Analysis Plan (SAP)**

The primary outcome was the mean implanted cup inclination and femoral stem anteversion difference between the VR and control groups. Other outcomes considered between groups included: a) the duration required to complete the task, b) the frequency of requesting assistance, and c) the number of errors made.

We used standard statistical methods to gather descriptive statistics. We conducted the Kolmogorov-Smirnov and Shapiro-Wilk tests to check whether the data followed a normal distribution. Our statistical tests were two-tailed, and we set the alpha level at 0.05. For continuous variables that were normally distributed, we used the two-sided independent sample t-test, while for those that weren't normally distributed, we used the Mann-Whitney U-test. We compared categorical data using the chi-square test. To determine if using VR had an impact on a student's task performance, a paired t-test was conducted to compare their outcomes with and without VR. We performed all statistical analyses using SPSS software (IBM, version 27.0).

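### Prior VR experience is surveyed before training, but no planned analysis uses it; reporting it by arm and adding it as one covariate is a nearly free, small improvement.

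*Combined protocol and SAP*

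**What the plan says.** Recruitment defines the population by student status and lack of surgical experience: "Eligible study participants included undergraduate medical students at our university with no previous surgical experience willing to participate". The exclusions cover postgraduates, students with earlier hip arthroplasty or general surgery experience, and the unwilling. Nothing there concerns earlier use of VR.

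Randomisation states: "All participants were then randomised in the VR or control group for cup and stem training and implantation by a computerised random number generator". No stratification or blocking is described. The arms mirror each other: a student who trains in VR for the cup is a control for the stem, and the reverse.

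VR training records the baseline item: "Before the VR-THA training, participants were asked to complete a survey evaluating their previous VR technology experience". All VR-trained students then complete three consecutive sessions.

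The Statistical Analysis Plan compares groups with an independent t-test or a Mann-Whitney test, and categorical data with a chi-square test. For the within-student question (VR against no VR) it states: "To determine if using VR had an impact on a student's task performance, a paired t-test was conducted to compare their outcomes with and without". It names no covariate, subgroup or interaction. It mentions descriptive statistics without listing variables.

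**The concern.** Of the baseline items collected, prior VR experience lies closest to the intervention. With a fixed number of sessions, a student used to a headset might spend more of them on the implant task; the documents do not say whether this happens. The survey suggests that the investigators thought the item relevant, yet it has no stated role afterwards.

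Two things are at stake, both modest. First, if experience predicts accuracy, an unadjusted comparison leaves explainable variance in the error term. Second, the arms are mirrored. If experience helps on both tasks, one chance imbalance would flatter VR in one task and disfavour it in the other. Without experience reported by arm, a reader could not tell that pattern from a real difference between cup and stem.

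**Working it through.** **The plan's own figure.** Power Analysis uses "To detect a difference of 20 degrees of implantation" and, from the first ten cup measurements, "the mean cup angle was 50.40 with a standard deviation of 18" degrees, and concludes: "with a two-sided alpha of 0.05 and power of 80%, at least 26 students were required in its group". The normal formula gives n = 2 × (18 × (1.960 + 0.842) / 20)² = 12.7, so 13 per group; an exact t-test gives 14. The stated 26 is not reproduced as a per-group number. It equals the total 2 × 13, and also the exact per-group number for an effect size of 0.80 (25.5, rounded up), the lower end of "an effect size of 0.80 to 0.90". The present point does not depend on which was meant.

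**Inputs.** SD 18° (Power Analysis; a cup figure, assumed here for the stem too). 101 students (Recruitment). Split 50/51 (assumed; no ratio is stated). Share with prior VR use, p = 0.1 to 0.5, and outcome gap between users and non-users, g = 0.25 to 0.8 SD, that is 4.5° to 14.4° (both assumed; the documents give neither).

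**Unadjusted standard error.** 18 × √(1/50 + 1/51) = 18 × 0.199 = 3.58°.

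**Chance imbalance, 95% range.** 1.96 × √(p(1−p)(1/50 + 1/51)):
- p = 0.1: 1.96 × 0.0597 = ±11.7 points
- p = 0.3: ±17.9 points
- p = 0.5: 1.96 × 0.0995 = ±19.5 points

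**The same in degrees.** Multiply by the gap:
- smallest case: 4.5 × 0.117 = ±0.5°
- largest case: 14.4 × 0.195 = ±2.8°

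This is a component of the 3.58° standard error, not an addition to it.

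**Adjusted standard error.** 3.58 × √(1 − R²), with R² = p(1−p)g²:
- p = 0.1, g = 0.25: R² = 0.09 × 0.0625 = 0.006, giving 3.57°
- p = 0.3, g = 0.5: R² = 0.21 × 0.25 = 0.052, giving 3.49°
- p = 0.5, g = 0.8: R² = 0.25 × 0.64 = 0.16, giving 3.28°

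The formula ignores the average variance cost of chance correlation between covariate and arm, about 1/(101 − 1) = 1%. At the lowest corner, where R² is 0.006, there is therefore no real gain.

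**Validity without adjustment.** In 20,000 simulated trials each, with g = 0.8 SD and no VR effect, the unadjusted t-test rejected at 0.054 (p = 0.3) and 0.051 (p = 0.5), against a nominal 0.05.

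**Power for a naive v experienced contrast.** With about 50.5 per arm, the interaction has SE = 18 × √(2/(50.5p) + 2/(50.5(1−p))): 7.2° at p = 0.5 and 11.9° at p = 0.1. Times 2.80, the interaction detectable with 80% power is about 20° to 33°, at least as large as the whole design difference of 20°.

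**The case against.** The strongest reply is that nothing is wrong. Chance imbalance is not bias, the test allows for it, and the largest shift above is small beside the 20° design difference. That stands, and it limits the point to precision and interpretation.

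A second reply also has force. If prior VR use matters only by making the headset sessions more productive, it modifies the VR effect and gives no reason for control students to differ. The precision argument needs experience to predict accuracy more generally, which the documents do not show. Hence the gain is described as possible only.

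Third, the paired test compares each student with themselves, so prior experience is balanced there. That stands, although VR status remains tied to which task was done.

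Fourth, the unlisted descriptive statistics might include the survey. They might; the plan does not say so.

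A reader might infer more than the documents support:
- *The unadjusted comparison is biased by uneven VR experience.* Allocation is random, and the simulated error rate stays near 0.05.
- *The trial fails because it cannot answer for VR-naive students.* The Objectives concern students without surgical experience. An effect averaged over a mix of VR experience is a valid answer to that question, and the sample could not support a naive v experienced test anyway.
- *The survey came only after students knew their assignment.* The text places it before VR training. Its order relative to notification is inferred from the sequence of sections.

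**Conclusion.** The gap is real and minor. A baseline answer close to the intervention is collected and has no named place in the analysis, while the between-group cup and stem comparisons are unadjusted. Using it would lower the standard error by between almost nothing and about 8% (1 − 3.28/3.58), and would let readers see whether the mirrored arms differed on it. The size rests on the assumed split, prevalence and gap, and on carrying the cup SD over to the stem. Validity of the planned tests is not in question.

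**What to change.** - Tabulate prior VR experience (none v any) by arm. Every student has VR for one task, so the survey should cover all 101; confirm this and state any missing answers.
- Fit a linear model for each cup and each stem between-group comparison, with arm and prior VR experience (none v any) as the only terms. State whether it replaces or accompanies the unadjusted test. The Mann-Whitney fallback takes no covariate, so the model would sit beside it.
- If outcomes have already been analysed, label the adjusted result post hoc.
- If effects are shown separately for VR-naive and VR-experienced students, label them exploratory and state the low power.
- Leave the paired comparison unadjusted for this item.

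The cost is one table row and one model term per comparison, with no new data. The document describes randomisation as done, so asking the question at the pretest and stratifying on it applies only to a future trial.
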